1. PROTOCOL SUMMARY

1.1 Protocol Synopsis

Title:	Post-Market Clinical Follow-Up Registry of the Integra External Ventricular Drainage Systems and Accessories
Short Title:	External Ventricular Drainage PMCF Registry
Protocol number:	C-EXTVDR-001
Study Description:	This post-market follow-up registry will capture clinical data specific to the safety and performance of the Integra External Ventricular Drainage Systems and Accessories.
Background:	
External Ventricular Drainage (EVD) Systems are a temporary system which allow drainage of cerebrospinal fluid (CSF) from the lateral ventricles of the brain. EVD Systems are commonly used within neurosurgery for the management of patients who require drainage of CSF.
 
EVD Systems are regularly used in neurosurgery for diagnostic and therapeutic purposes.
 
Complications of EVD Systems are well recognized, with infection and hemorrhage being the most common ones related to these procedures, followed by ventriculostomy occlusion.
 
The rate of EVD-associated hemorrhage ranges from 18 to 41% in adults as reported in literature, and in pediatric population (single center), it has been found that incidence of hemorrhage at EVD placement to be 10%, and the incidence of hemorrhage on EVD removal to be 21.9%. Studies have demonstrated non patent EVDs in 19-47% of patients.

Pre/Post-Market:	Post-Market Clinical Follow-Up Registry
Study Design:	Observational, multi-center, post-market registry
Primary Objective:	The primary objective of this registry is to capture clinical performance data to confirm the continued performance of the Integra External Ventricular Drainage Systems and Accessories.
Safety Objective:	The safety objective of this registry is to capture clinical safety data to confirm the continued safety of the External Ventricular Drainage Systems and Accessories.
Primary Endpoint:	The primary endpoint is anticipated drainage (i.e., observed drainage consistent with the patient's clinical presentation) of cerebrospinal fluid (CSF) in the clinical setting until the EVD System is no longer required.

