5.5 Primary Study Hypothesis

The primary hypothesis is to evaluate the success rate of CSF drainage against a pre-defined performance goal of 80% (with an expected success rate of 90% or higher). The hypothesis will be tested based on patients of all ages using the exact method along with two-sided 95% confidence interval.

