6 STUDY POPULATION

6.1 Inclusion Criteria

In order to be eligible to participate in this study, Patients must meet all of the following criteria:

1. Patient and/or legally authorized representative has agreed to participate in the study by signing the EC-approved consent form, where applicable.
2. Patients (of any age) who underwent or who plan to have a procedure with one of the Integra or Codman External Ventricular Drainage as distributed by Integra System.
3. For patients who have had the EVD System removed prior to study enrollment, have available follow-up data from implant until the EVD System is no longer required for drainage and monitoring of CSF.

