9.4.1 Anticipated Adverse Device Effects

Complications which may result from the use of the EVD systems include the risks associated with the medications and methods utilized in the surgical procedure, as well as the patient's degree of intolerance to any foreign object implanted in the body.

The principal complications associated with cerebrospinal fluid drainage are Catheter obstruction, infection (including meningitis and ventriculitis), intracranial hypotension/hypertension, migration of ventricular Catheters, ventricular collapse, and intracerebral hemorrhage.

Excessive lowering of ICP in infants may result in complications which include subdural hematomas, markedly sunken fontanelles, overriding of cranial bones, and conversion of a communicating to a non-communicating hydrocephalus.

Ventricular Catheters may be obstructed by particulate matter such as blood clots, fibrin, or brain fragments. If not properly located in the lateral ventricle, the ventricular Catheter may become embedded in the ventricular wall or choroid plexus. Less commonly, the ventricular Catheter may be obstructed by the excessive reduction of ventricular size to slit like proportions.

Complications that are specific for the use of the Cranial Access Kits are improper use of the hand drill including failure to properly secure the drill bit to the variable chuck or failure to properly secure the depth guard to the drill bits. Improper use of the hand drill may result in serious injury. Bleeding may occur at the site of the drill hole, originating from the scalp, bone, dural, or cerebral areas. Due to the possibility of cerebral or extra cerebral hemorrhage or any other complication of this procedure, drill hole placement is the sole responsibility of the attending neurosurgeon.

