11.4.9 Sub-Group Analyses

Subgroup analyses will be performed for drainage systems for primary endpoint and secondary endpoint. The purpose of the subgroup analysis is not to reach statistically significant results within each subgroup, but rather to assess the consistency and robustness of the treatment effects across the subgroups. Descriptive statistics will be used for the subgroup analysis. Two-sided 95% confidence intervals will be reported as appropriate for reference purpose only. No multiplicity adjustment will be considered for the subgroup analysis.

EVD Systems:

- AccuDrain
- Hermetic Plus
- LimiTorr
- MoniTorr
- Codman EDS 3 / EDS 3C
- Basic CSF Drainage System
- External Ventricular Drainage System

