8.10.1. Adverse Events

All AEs and complications occurring from the time of subject enrollment until study termination or study completion include intra-operative AEs and complications. AEs will be coded using the Medical Dictionary for Regulatory Activities (MedDRA) terminology for data summaries. Each AE will be coded with 2 levels including Preferred Term (PT) and System Organ Class (SOC). The severity of all adverse events will be reviewed and adjudicated and classified as mild, moderate or severe.

The total number of device-related AEs as well as the percentage of patients with at least one device-related AE will be presented overall and by SOC and PT. AEs will also be tabulated by severity and by relationship to device within each SOC and PT. A listing of device-related AEs and SAEs will be presented respectively.

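### No planned safety table gives the proportion of patients with any device- or procedure-related hemorrhage, because patient percentages are limited to device-related AEs by single term and organ class

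*SAP*

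**What the plan says.** **Endpoint and objective.** The safety objective (protocol 3.2, SAP 4.2) is to confirm that the devices remain safe. The first safety endpoint (protocol 3.6, SAP 5.4) is adverse events related to the device or to the procedure.

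**Planned tables.** SAP 8.10.1 codes each event at two levels, preferred term (PT) and system organ class (SOC). It gives the number of device-related events, and the "percentage of patients with at least one device-related AE will be presented overall and by SOC and PT". Events are also tabulated by severity and by relationship to the device within SOC and PT, and device-related AEs and SAEs are listed. Protocol 11.4.6 has the same structure. SAP 8.10 puts all safety summaries on the Full Analysis Set and plans no formal safety test.

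**Subgroups.** Protocol 11.4.9 states: "Subgroup analyses will be performed for drainage systems for primary endpoint and secondary endpoint". No outcome is split by age. Age appears only as a baseline variable (SAP 8.3), although eligibility is "Patients (of any age) who underwent or who plan to have a procedure" and, for the primary endpoint, "The hypothesis will be tested based on patients of all ages".

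**Hemorrhage in the protocol.** The synopsis background places infection and hemorrhage first among complications, followed by occlusion. It says "The rate of EVD-associated hemorrhage ranges from 18 to 41% in adults as reported in literature". For children, from a single center, it gives the "incidence of hemorrhage at EVD placement to be 10%, and the incidence of hemorrhage on EVD removal to be 21.9" per cent. It also reports non-patent drains in 19-47% of patients. Protocol 9.4.1 lists intracerebral hemorrhage as a principal complication, subdural hematomas under excessive lowering of pressure in infants, and for the Cranial Access Kit: "Bleeding may occur at the site of the drill hole, originating from the scalp, bone, dural, or cerebral areas".

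**The concern.** A reader of the final report will want to know how many patients bled because of the device or its placement. The planned tables fall short of that in two ways.

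1. **Scope.** The planned patient percentage covers device-related events only. Bleeding attributed to drilling or insertion but not to the device belongs to the safety endpoint and has no planned percentage.
2. **Grouping.** PT rows are too narrow if bleeding at different sites is coded to different terms. SOC rows are too broad, because they mix bleeding with other events. Nothing in between is planned.

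Without a prespecified group, a hemorrhage rate would be assembled after the data are seen, and the choice of terms would be open to selection. If it is not assembled at all, the visible rows understate bleeding whenever it is spread over more than one term.

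**Working it through.** **Denominator.** The documents give no design figure for hemorrhage or for any other adverse event. The only design figure is for the primary endpoint: 110 evaluable and 120 enrolled with 8% dropout (SAP 7.2). It reproduces closely. With 110 patients, the exact two-sided 95% lower limit exceeds 80% from 97 successes upward, and power at the expected 90% success rate (protocol 5.5) is 79.1%, against the stated 80%. For dropout, 110 / (1 - 0.08) = 119.6, so 120. I use 110 as the denominator below.

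**What the planned outputs contain.**

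| Output (SAP 8.10.1, protocol 11.4.6) | Patients with any hemorrhage? | Procedure-related events counted? | Age split? |
|---|---|---|---|
| % with a device-related AE, overall | No, all events mixed | No | No |
| The same by SOC | No, mixed with other events | No | No |
| The same by PT | Only if all bleeding has one PT | No | No |
| Severity and relationship within SOC and PT | No | Not as a category; relationship is to the device | No |
| Listings | Not a rate | Planned for device-related AEs and SAEs | No |

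**Why PT rows cannot be summed.** Let A and B be the numbers of patients with each of two bleeding terms. The number with either is A + B minus the number with both, and the table does not show the number with both. With A = B = 11, patients with any hemorrhage number from 11 (complete overlap) to 22 (no overlap), that is 10.0% to 20.0% of 110. The two rows are compatible with every value in that range.

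**How far one row can understate.** Assume 22 of 110 patients bleed, over two equal terms without overlap. The documents give neither the split nor the rate in this registry. Exact (Clopper-Pearson) 95% intervals:

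- Any hemorrhage: 22/110 = 20.0% (13.0 to 28.7).
- Each PT row: 11/110 = 10.0% (5.1 to 17.2).

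The row is half the true proportion, and its interval lies wholly below 20%. An uneven split gives a larger top row, and coding to one PT removes the effect.

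**Precision of a grouped rate.**

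- If all 110 were adults: 20/110 gives 11.5% to 26.7%, and 45/110 gives 31.6% to 50.7%. These counts correspond to the ends of the quoted 18-41% range.
- The documents give no pediatric share. Assuming 11, 22, 28 or 55 children and a rate near 10%: 1/11 gives 0.2% to 41.3%; 2/22 gives 1.1% to 29.2%; 3/28 gives 2.3% to 28.2%; 6/55 gives 4.1% to 22.2%.

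The overall rate would be usefully precise. A pediatric rate would be descriptive only.

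**Age.** Only year of birth is collected (protocol 8.2). Placement year minus birth year equals either the true age or the true age plus one, so patients with a difference of exactly 18 cannot be classified with certainty.

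**The case against.** The strongest case on the other side has five parts.

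- **The literature figures are background.** No section makes them benchmarks, the only declared comparator is the 80% drainage goal, and no safety test is planned. This stands. A reader might infer that the registry must test its hemorrhage rate against 18-41%, or that these are the only safety figures given. Neither is supported: the synopsis also gives 19-47% non-patency and 21.9% pediatric bleeding on removal.
- **A count can be made later.** The device-related AE and SAE listings, and the by-subject listings in protocol 11.4.10 and SAP 8.1, allow patients with bleeding to be counted once each. This stands. To infer that the report cannot address hemorrhage at all would go too far. What is missing is a planned rate with a fixed definition.
- **Dilution is not certain.** 9.4.1 names one hemorrhage term among its principal complications and ties the other sites to infants or to the access kit. This stands in part: the size of the effect is an assumption. That rows cannot be summed does not depend on it.
- **A signal in children would hardly be detectable.** This stands. It is tempting to argue that pooling would hide a rise in children from the quoted 10% to some higher rate. But 10% is the placement figure only, and events are collected until the drain is no longer required. Judged against the 21.9% on removal, most of such a rise disappears.
- **An all-cause group would mislead.** Many patients receive a drain because they have bled, and deterioration of a baseline condition is recorded as an event (protocol 9.6). This stands, and it is why the group should be limited to related events.

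Catheter obstruction is already partly covered by the tertiary endpoints on failure, replacement and flushing, so that group matters less than hemorrhage.

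**Conclusion.** The point holds as a gap in prespecification. The planned patient percentages are narrower than the safety endpoint, since they omit procedure-related events. They also yield no proportion of patients with any related hemorrhage unless all bleeding is coded to one preferred term. Under the stated assumption of two equal, non-overlapping terms, a 20.0% rate would appear as two rows of 10.0%.

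The omission of procedure-related events and the fact that rows cannot be added follow from the text alone. The halving rests on an assumed split and an assumed rate. The value of an age split rests on a pediatric share that the documents do not give; it is worth showing because patients of any age are enrolled, not because it could establish a difference. The primary analysis and the sample size are unaffected. The change should be made before database lock.

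**What to change.** In SAP 8.10.1:

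1. Present patient percentages for device- or procedure-related AEs, to match the safety endpoint, and keep the device-related table beside them. State which procedures count, because protocol 9.3 confines procedure-relatedness to procedures specific to the registry, while section 2.3 adds none to standard care.
2. Add two event groups, hemorrhage and catheter obstruction, each defined by a preferred-term list fixed before database lock.
3. Count each patient once per group. Give n, % and exact 95% CI, overall and descriptively for under 18 and 18 or over, with a note that age is approximate. Split hemorrhage by placement versus removal where this is recorded.
4. If the synopsis figures are shown alongside (adults 18-41%; children 10% at placement and 21.9% on removal; non-patency 19-47%), label them as context and not as a benchmark.
5. If an all-cause hemorrhage row is shown, keep it separate and note that bleeding from the underlying disease enters it.

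The cost is a term list and a few extra tables from data already planned for collection, with no added patients. The drawback is wide intervals in children, such as 1.1% to 29.2% for 2/22.

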8.10.2. Device Deficiencies

Device deficiencies will be summarized using descriptive statistics. A listing of device deficiencies will be presented.

8.11. STATISTICAL ANALYSIS AND GENERAL DATA ISSUES

8.11.1. General Calculations and Data Conventions

Relative Day

The date the EVD device placement will be considered relative day 0, and the day before the device placement will be relative day -1. Relative days will be calculated as follows only when the full assessment date is known (i.e., partial dates will have missing relative days): For days on or after the device is implanted: Relative Study Day (Rel Day) = Date of Assessment – Date of implant. For days before the device is implanted: Relative Study Day (Rel Day) = Date of Assessment – Date of implant.

Age

Age will be presented as the number of years between date of birth and date of signing the informed consent. Age is computed in whole years as follows:

$$\text{Age (years)} = \text{year of informed consent} - \text{year of birth}$$

Length of Time

Except for age, the length of time between 2 reference dates will be calculated as the number of Calendar days between the two dates. When the length of time between 2 reference dates is expressed in months, the number of months will be calculated as the number of calendar days between the 2 dates divided by 30.4 days. When the length of time between 2 reference dates is expressed in weeks, the number of weeks will be calculated as the number of calendar days between the 2 dates divided by 7 days.

Clinical Trial Duration

Clinical Trial duration will be calculated as the total number of days each subject is in the clinical trial.

$$\text{Clinical Trial Duration (days)} = (\text{date of last clinical or adverse event visit or withdrawal} - \text{date of EVD placement}) + 1$$

Duplicate Data

For unscheduled duplicate data within a protocol-specified visit, the last measured value will be used for the analysis. If it is not possible to identify the “last measured value” the average of the duplicate values will be used.

Partial AE and medication date

For partial start dates:

1. If the year is unknown, then do not impute the date but assign a missing value
2. If the month is unknown, then:
 - a. If the year matches the year of initial EVD placement, then impute the month and day of the EVD placement date.
 - b. Otherwise, assign "January."
 - c. If the day is unknown, then
 - d. If the month and year match the month and year of the initial EVD placement date, then impute the day of the surgery date.
 - e. Otherwise, assign "01."

For partial end dates:

1. If the year is unknown, then do not impute the date but assign a missing value.
2. If the month is unknown, then assign "December."
3. If the day is unknown, then assign the last day of the month.

